12. OTHER ANALYSES

12.1 Pharmacokinetic and Pharmacodynamic analyses

Plasma concentrations will be used to perform non-compartmental analysis (NCA) as appropriate. Further details of the pharmacokinetic modeling and simulation will be documented in a PK population analysis plan (PAP). Statistical Analysis of Pharmacokinetic and Pharmacodynamic Data

All of the PK/PD analyses will be performed using the PK/PD Set.

Summary statistics (number of observations, mean, standard deviation, coefficient of variation, median, maximum, minimum, and geometric mean) will be determined for all PK/PD parameters derived by NCA, as appropriate.

Plasma concentrations of C1 INH antigen, C1 INH functional activity, C4 and C1 q at each nominal sampling time with and without baseline-adjustment will also be summarized using descriptive statistics (number of observations, mean, standard deviation, coefficient of variation, median, maximum, minimum, and geometric mean).

12.2 C1 INH Antibody

Results of C1 INH antibody testing will be summarized by treatment and visits, and listed by individual subjects for the Safety Set.

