In Study 0624-206, a total of 21 (45%) subjects had detectable anti-rHuPH20 antibodies during the study, with 15 (32%) of the 21 subjects having a post-baseline titer of $\geq 1:20$. All samples from these subjects were determined to be negative for rHuPH20-neutralizing activity. As requested by the FDA, the sponsor followed subjects who had treatment-emergent titers of $\geq 1:20$ for 1 year post-treatment. There were no clinical sequelae observed in any subject and all titers declined during longitudinal follow-up. Three subjects in Study 0624-102 had reportable anti-rHuPH20 antibodies at a titer $\geq 1:20$; however, in all 3 cases, subjects had antibodies to rHuPH20 present at baseline (prior to the first dose of study drug). Subjects were not asked to participate in longitudinal follow-up, as anti-rHuPH20 antibody titers remained at or below the baseline level for each subject by the end of the study.

In Study SHP616-103, a total of 26 healthy volunteers were enrolled in the study. Twenty-three (23) subjects received a single SC dose of both 1000 and 2000 IU, and 1 subject only received a single SC dose of the 1000 IU C1 esterase inhibitor [human] liquid for injection. Therefore 24 unique subjects have been exposed to 47 doses of C1 esterase inhibitor [human] liquid for injection.

Subcutaneous administration of 1000 IU and 2000 IU C1 esterase inhibitor [human] liquid for injection was generally well tolerated and the clinical safety data were consistent with previous CINRYZE IV or SC studies. Overall 19 (73.1%) of the 26 subjects reported at least 1 TEAE in the study: 62% (16/26), 29% (7/24), and 44% (10/23) of subjects administered 1000 U IV CINRYZE, 1000 IU and 2000 IU of SC C1 esterase inhibitor [human] liquid for injection, respectively.

With regard to the local tolerability of SC administration of 1000 IU and 2000 IU C1 esterase inhibitor [human] liquid for injection, there was no clear difference in the overall incidence of injection site reactions with respect to dose (1000 IU versus 2000 IU). Twenty-three of 24 (95.8%) subjects reported injection site reactions, all were mild (58.3%) to moderate (37.5%) in severity, and the majority resolved within 2 hours postdose. The majority of reported reactions were erythema (mild or moderate) and a warm sensation (all mild).

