2.2.2 Secondary Objectives

The key secondary objectives are to demonstrate the superior efficacy of SC administration of 2000 IU C1 esterase inhibitor [human] liquid for injection for the prevention of angioedema attacks relative to placebo as measured by:

1. The proportion of subjects meeting the criterion of at least a 50% reduction in the NNA during the 2000 IU C1 esterase inhibitor [human] liquid for injection treatment period relative to the placebo period.
2. The NNA during each treatment period excluding the first 2 weeks.
3. The proportion of subjects meeting the criterion of at least a 50% reduction in the NNA for the 2000 IU C1 esterase inhibitor [human] liquid for injection treatment period relative to the placebo period excluding the first 2 weeks of each treatment period.

Other secondary objectives are:

- To assess the proportion of responders during treatment with 2000 IU C1 esterase inhibitor [human] liquid for injection relative to treatment with placebo, where the proportion of responders is defined as achieving at least a 50% reduction in the NNA during a treatment period relative to the pretreatment assessment (ie, the subject's attack rate without prophylactic treatment)
- To assess the severity of angioedema attacks during treatment with 2000 IU C1 esterase inhibitor [human] liquid for injection relative to treatment with placebo
- To assess the number of attack-free days during treatment with 2000 IU C1 esterase inhibitor [human] liquid for injection relative to treatment with placebo
- To assess the number of angioedema attacks requiring acute treatment during treatment with 2000 IU C1 esterase inhibitor [human] liquid for injection relative to treatment with placebo
- To assess the safety and tolerability of SC administration of 2000 IU C1 esterase inhibitor [human] liquid for injection
- To assess the immunogenicity of SC administration of 2000 IU C1 esterase inhibitor [human] liquid for injection
- To characterize the PK and PD of SC administration of 2000 IU C1 esterase inhibitor [human] liquid for injection
- To assess the clinical response and safety/tolerability of icatibant (Firazyr[®]) for the treatment of acute angioedema attacks (applicable for subjects ≥ 18 years of age)

- To assess disease activity as measured by the Angioedema Activity Score (AAS)
- To evaluate subject experience with self-administration of SC 2000 IU C1 esterase inhibitor [human] liquid for injection

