3.1 Study Design and Flow Chart

This is a randomized, double-blind, placebo-controlled, two-period, three-sequence, partial crossover study (Figure 7). The design was chosen to optimally address the joint protocol objectives of establishing efficacy (relative to placebo) and safety (ie, enrolling an adequate number of subjects to have precision of estimation to detect or rule out safety signals).

Additionally, this design maximizes the number of subjects exposed to C1 esterase inhibitor [human] liquid for injection and minimizes subject exposure to placebo, while having adequate subject exposure to placebo to assess efficacy.

Subjects will be screened within 21 days prior to randomization. Subjects are required to have a history (based on subject recall and medical records) of ≥ 2 attacks per month on average per inclusion criterion #3. At least 66 eligible subjects will be randomized to 1 of 3 treatment sequences prior to the first dose of investigational product in Treatment Period 1 (ie, Dosing Day 1a) using interactive response technology (IRT). Randomization of subjects will be stratified by use of prophylactic therapy with C1 INH at the time enrollment.

Figure 7 Study Design Flow Chart

Each treatment period will be 14 weeks, without a washout between the 2 periods. The omission of a washout period is to minimize the duration that subjects will be without active treatment. It is recommended that the twice weekly dosing schedule (every 3 or 4 days) be maintained between the last dose of investigational product in Treatment Period 1 and the first dose of investigational product in Treatment Period 2. Every effort should be made to complete scheduled dosing and to avoid situations where investigational product is not received. In order to prevent a missed dose, a less than 3-day interval may occur, with the recommendation of allowing at least 24 hours between doses.

All study site personnel, subjects, qualified home health professionals, and the sponsor will be blinded to treatment sequence.

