7.1.3.1 Visit 1b (predose)

The following procedures will be performed at the investigative site prior to the first dose of investigational product in Treatment Period 2 at Visit 1b:

- Collection of AEs
- Physical examination
- Vital signs (\leq 30 min before the start of injection)
- Clinical laboratory testing (biochemistry, hematology, coagulation)
- Urinalysis testing with microscopy
- Urine pregnancy test (in females of childbearing potential)
- Recording of concomitant medications
- PK (C1 INH antigen, C1 INH functional) and PD (C4) sampling (within \approx 15 min)
- Immunogenicity (anti-C1 INH antibody) blood sample collection
- AE-QoL, EQ-5D-5L, WPAI-GH, and SDS assessments recorded in the electronic subject diary
- HRUA-HAE

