9.9 Safety Analyses

Adverse events will be coded using the MedDRA. The number of events, incidence, and percentage of TEAEs will be calculated overall, by system organ class, preferred term, and treatment. Treatment-emergent AEs will be further summarized by severity and relationship to investigational product. Adverse events related to investigational product, AEs leading to withdrawal, AEs of special interest, SAEs, and deaths will be similarly summarized/listed.

Clinical laboratory tests (hematology, chemistry, and coagulation), vital signs, and ECG findings will be summarized by treatment and visit. Potentially clinically important findings will also be summarized or listed.

The incidence and severity (mild, moderate, severe) of SC injection site reactions will be summarized by treatment and visit. The overall impact of injection site reactions on daily living (yes/no) and duration will be summarized by treatment.

Results of C1 INH antibody testing will be reported for individual subjects.

The tolerability of icatibant therapy for acute angioedema attacks will be summarized.

To assess the influence of any carryover effect on adverse reporting, a sensitivity analysis may be conducted by attributing TEAEs that occur during the first 2 weeks of Treatment Period 2 to Treatment Period 1 for the A/B (C1 INH to placebo) treatment sequence. In other words, C1 esterase inhibitor [human] liquid for injection may account for any TEAEs in the first 2 weeks of the placebo treatment, when the carryover effect (if present) is suspected to be maximal.

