TEAEs related to investigational product, serious TEAEs related to investigational product and TEAEs related to investigational product leading to withdrawal will be similarly summarized as TEAEs. Summaries of TEAE or TEAE related to investigational product within 24 hours after the end of injection of investigational product will be provided by treatment.

A sensitivity analysis will be conducted by attributing TEAEs that occur during the first 2 weeks of Treatment Period 2 to Treatment Period 1 for the A/B (C1 INH to placebo treatment sequence.

To assess carryover effect with an assumption that it exists for both A/B and B/A treatment sequences, a sensitivity analysis will be conducted by excluding any TEAEs occurring within the first 2 weeks of Treatment Period 2, when carryover is suspected to be maximal.

All information about AEs collected on the eCRF will be listed alongside the treatment, preferred term, and SOC. Listings will also be provided on TEAEs related to investigational product, TEAEs leading to withdrawal, SAEs, and deaths.

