2. STUDY DESIGN

2.1 Study Design Overview

Data will be collected in Study SHP616-300, a phase 3, randomized, double-blind, placebocontrolled, two-period, three-sequence, partial crossover study to evaluate the efficacy and safety of SC administration of 2000 IU of C1 esterase inhibitor [human] liquid for injection for the prevention of angioedema attacks in adolescents and adults with HAE. The trial uses a partial Balaam's cross-over study design with two periods (each lasting 14 weeks), two treatments (active and placebo), and three treatment sequence groups (Exhibit A). The Study Design Flow Chart is shown in Exhibit B.

This multicenter study is being conducted at approximately 40 sites globally (North America and EMEA). The study aims to screen 75 subjects, enroll 66, and ensure that 54 subjects complete both study periods. Treatment sequence groups 1 (AB) and 2 (BA) will each contain 26 subjects, with treatment sequence 3 (AA) containing 14 subjects.

Treatment Sequence	Treatment Period 1	Treatment Period 2	Approximate Number of Subjects Randomized
1 (AB)	А	В	26
2 (BA)	В	А	26
3 (AA)	А	А	14

Exhibit A: Treatment Sequences

Treatment A: 2000 IU (4.0 mL) C1 esterase inhibitor [human] liquid for injection administered SC twice weekly (every 3 or 4 days) for 14 weeks.

Treatment B: Placebo (4.0 mL) administered SC twice weekly (every 3 or 4 days) for 14 weeks.

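### The by-treatment antibody summary in SAP 12.2 puts A/B subjects already exposed to active drug in the placebo column at every Period 2 visit, with no rule for attributing positives found after crossover

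*SAP*

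**What the plan says.** Immunogenicity is one of the other secondary objectives (Protocol 2.2.2): "To assess the immunogenicity of SC administration of 2000 IU C1 esterase inhibitor [human] liquid for injection". The main SAP's plan for summarising it is one sentence in 12.2: "Results of C1 INH antibody testing will be summarized by treatment and visits, and listed by individual subjects for the Safety Set". Protocol 9.9 promises subject-level reporting ("Results of C1 INH antibody testing will be reported for individual subjects"), and the protocol synopsis adds a summary.

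On the design, Protocol 3.1 says "Each treatment period will be 14 weeks, without a washout between the 2 periods". Antibody samples are taken predose at Visits 1a, 8a, 16a, 24a and 27a or 28a, then predose at 1b, 8b, 16b, 24b and 28b, and again at 1 week and 1 month after treatment (Protocol 7.1.2 to 7.1.5). The Visit 1b list in Protocol 7.1.3.1 names the sample explicitly: "Immunogenicity (anti-C1 INH antibody) blood sample collection".

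SAP 11 names antibody status as a safety endpoint and fixes one baseline for all safety analyses, the last assessment before the first Period 1 dose. SAP 11.1 deals with carryover for adverse events: "A sensitivity analysis will be conducted by attributing TEAEs that occur during the first 2 weeks of Treatment Period 2 to Treatment Period 1" in the A/B sequence. A second analysis drops events from those two weeks. SAP 12.2 has no counterpart for antibodies.

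**The concern.** Labelling a result by current treatment works when the response belongs to the drug being given at the time. An antibody response need not stop when the drug does. After crossover in the A/B sequence, a positive sample labelled placebo may have been produced by the 28 active doses of Period 1. The SAP accepts this problem for adverse events but leaves antibodies on the current-treatment label.

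Three things are left open: what counts as a treatment-emergent antibody, which period the predose Visit 1b sample belongs to, and how positives found after crossover or during follow-up are attributed. At stake is how far the summary table answers a stated objective. A reader who looks at the Period 2 columns could take drug-induced antibodies for background, and a subject who converts late in the A/B sequence would be missing from the active count.

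**Working it through.** **Inputs.** Planned allocation, from the HRQoL SAP 2.1: "Treatment sequence groups 1 (AB) and 2 (BA) will each contain 26 subjects, with treatment sequence 3 (AA) containing 14 subjects". Protocol Table 7 gives the same numbers. Twice-weekly dosing for 14 weeks is 28 doses per period. Sampling visits are as listed above; as a check, 5 (Period 1) + 5 (Period 2) + 2 (post-treatment) + 1 (early discontinuation) = 13, which agrees with Protocol Table 9. The plan states no figure for the antibody analysis itself, so there is none to reproduce.

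**Who is in each column, by visit (full retention assumed).** Active study-drug doses already received are in brackets.

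| Visit | Active column | Placebo column |
|---|---|---|
| 8a to 28a | A/B 26 + A/A 14 = 40 | B/A 26 (0) |
| 1b predose, if given the Period 2 label | B/A 26 (0) + A/A 14 (28) = 40 | A/B 26 (28) |
| 8b predose | B/A 26 (7) + A/A 14 (35) = 40 | A/B 26 (28) |

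At Period 1 visits the placebo column is free of study drug. At Period 2 visits it is entirely post-active.

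**Assumptions.** The documents give no anti-C1 INH rate. Let p be the proportion induced by active drug, with p = 10% for illustration and a range of 2% to 20%. Assume zero background and full persistence unless stated.

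**Period 1 visits, once conversion is complete.** Active p, placebo 0. The contrast is p, undistorted.

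**Visit 1b with the Period 2 label.** Placebo = p = 10%. Active = (26 × 0 + 14 × p)/40 = 0.35p = 3.5%. The contrast is reversed. Over the range it reads 2% against 0.7% (p = 2%) up to 20% against 7% (p = 20%).

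**Late Period 2 visits, once B/A subjects have also converted.** Placebo = p; active = (26p + 14p)/40 = p. The contrast is zero although the drug induced every antibody. With 50% persistence in A/B, placebo = p/2.

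**A/B subjects first detected after crossover.** Let q be the share of A/B converters first detected at a Period 2 visit. A cumulative count under current treatment gives active = [26p(1 − q) + 40p]/66, a loss of 26q/66 relative to p:

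- q = 0.25: 9.8%
- q = 0.5: 19.7%
- q = 1: 39.4% (an extreme case)

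**Pooling over visits, which SAP 12.2 does not specify.** The placebo column would hold 52 subjects, 26 of them previously on active. With q = 0, placebo = 26p/52 = p/2 and active = p, so 5% against 10%. With 50% persistence, placebo = p/4 = 2.5%.

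**The case against.** The strongest reply is that the summary is by treatment and by visit. Visits carry a and b labels, and SAP 11.2 lists them as separate time points for laboratory summaries. Exposed and unexposed placebo samples therefore never mix within a visit, and Period 1 supplies a clean parallel comparison in which A/B subjects who convert are counted under active. This stands. A reader might infer that the plan masks the immunogenicity of active drug, or that its table would show a halved contrast. The documents support neither: the halving needs pooling over visits, which SAP 12.2 does not call for.

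It is also fair to say that persistence is assumed. The titer follow-up in Protocol 1.2.1.1 concerned antibodies to rHuPH20, a different protein, and reported that "There were no clinical sequelae observed in any subject and all titers declined during longitudinal follow-up". It shows that antibodies can be followed after treatment; it gives no rate or duration for anti-C1 INH antibodies.

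Subject listings keep sequence and timing traceable, the baseline is already set in SAP 11, and the table shells are in a separate document not available here. No section states that Visit 1b antibody results take the Period 2 label. Prior C1 INH prophylaxis or rescue C1 INH could also produce positives.

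None of this makes the Period 2 contrasts interpretable or supplies an attribution rule. SAP 17.1 contains a sequence-by-period layout but does not assign it to this table, and its general layout for treatment-period safety tables is Treatment A against Treatment B. Listings leave each reader to decide attribution after unblinding.

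**Conclusion.** The concern holds for Period 2 visits and for A/B subjects first detected positive after crossover. Followed as written, SAP 12.2 compares post-active subjects labelled placebo with a mixture of newly and continuously treated subjects. If antibodies persist, the active-placebo contrast at those visits is diluted, can fall to zero, and at Visit 1b can reverse (10% against 3.5% under the stated assumptions and a Period 2 label). Late A/B converters are not credited to active; the size of that loss depends on an unknown q.

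Active immunogenicity is not masked overall, because the Period 1 comparison is sound. All percentages rest on assumed induction, zero background, the stated persistence and full retention. The table is descriptive, so the primary analysis, alpha and power are untouched. It should still be corrected, because this sentence is all the main SAP offers for summarising the immunogenicity objective.

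**What to change.** Amend SAP 12.2 as follows:

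- Tabulate antibody results by sequence and period, using the column layout already in SAP 17.1.
- Define treatment-emergent antibody against the pre-dose Period 1 baseline already set in SAP 11.
- Add cumulative incidence among all subjects ever exposed to active study drug, counting positives first detected after the first active dose.
- Use B/A samples up to and including predose Visit 1b as the reference unexposed to study drug, and flag prior or rescue C1 INH use for each positive.
- Assign predose Visit 1b samples to Period 1.
- State how the 1-week and 1-month samples are attributed.

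The cost is revised wording and table shells. The placebo reference falls to about 26 subjects, so its rate will be imprecise. No new samples are needed.

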12.3 Health-related Quality of Life Analyses

Details of the health-related quality of life analyses will be documented in a quality of life SAP. The health-related quality of life analyses will be summarized using the Full Analysis Set.

The AE-QoL is a questionnaire on the quality of life of patients suffering from recurrent angioedema. It consists of 17 specific questions that are associated with work, physical activity, free time, social relations, and food. Subjects will be asked how often they were restricted by— as well as the difficulties and problems that could be associated with—recurrent swellings (angioedema) during the previous 4 weeks. The result of the AE-QoL questionnaire is specified as a secondary efficacy endpoint (see Section 10.3).

The EuroQol 5-dimensional 5-level descriptive system (EQ-5D-5L) is a descriptive system of health-related quality of life states consisting of 5 dimensions (mobility, self-care, usual activities, pain/discomfort, anxiety/depression), each of which can take 1 of 5 responses. The responses record 5 levels of severity within a particular dimension. Results of the EQ-5D-5L health status instrument will be summarized on each question using descriptive statistics in accordance with the EQ-5D-5L user guide (version 2.0) by treatment and visit.

The Work Productivity and Activity Impairment-General Health (WPAI-GH) questionnaire includes 6 questions about work and activity impairment due to health problems during the past 7 days. Outcomes are expressed as impairment percentages, with higher numbers indicating greater impairment and less work or productivity. Results of the WPAI-GH questionnaire will be summarized on each question using descriptive statistics by treatment and visit.

CONFIDENTIAL

Shire SHP616-300 Statistical Analysis Plan idursulfase IT

Study personnel will ask subjects specific questions regarding their utilization of health care resources for the management of their HAE disease. Assessment (HRUA-HAE) will be completed at the time points specified protocol. Study personnel will enter the survey response into the eCRF. Results of the HRUA-HAE will be summarized on each question using descriptive statistics by treatment and visit.

12.4 Surveys on SC Administration and Self-administration of Investigational Product

Subjects will be asked to rate their overall experience in receiving twice weekly SC injections of investigational product. Subjects who have previously received C1 INH products via IV administration will be asked to indicate the preferred route for medication administration.

Those subjects, who choose to self-administer the investigational product during Treatment Period 1 or 2 under supervision, will be asked specific questions about their experience with self-administration of SC administration of C1 INH.

Results of the surveys for subject acceptability of SC administration and subject experience with self-administration of investigational product will be summarized by treatment and period using the Full Analysis Set.

